***Neurological assessments and subject interview:***

(Within 14 days prior to index procedure)

- Medical History
- Clinical Assessment/Physical Exam/Vital Signs
  - Within 14 days prior to the index procedure, and during the index procedure (both pre-treatment and immediately post-treatment)
- Relevant prior medications: indicate all antithrombotic (including anti-platelets, anticoagulants, and fibrinolytics) and inhibitors of ADP-induced platelet aggregation medications the subject has taken within 14 days prior to index procedure:
- Neurological evaluations performed by qualified personnel. Included as part of this examination are the NIH Stroke Scale Score (NIHSS), Modified Rankin Scale (mRS), and clinical neurological evaluations.

***Clinical Laboratory Tests:***

(Within 14 days prior to index procedure)

- Serum creatinine

***CT or MRI***

- Obtain an axial CT or MRI of the patient (performed within the last 10 years provided that the CT or MRI was not performed before the subject's 20th birthday) that shows the orbital anatomy of the skull. The CT/MRI should contain a valid centimeter marker and upload to Image Management Vendor (to be used for calibrating images). The CT/MRI scans are needed only for calibration and will not need interpretation.

## 6.2 Procedure

### **6.2.1 Indications for Use – Study Device**

The CODMAN ENTERPRISE Vascular Reconstruction Device and Delivery System is intended for use with embolic coils for the treatment of unruptured wide-neck, intracranial, saccular anterior circulation aneurysms ( $\leq 10$  mm) arising from a parent vessel with a diameter of  $\geq 2.5$  mm and  $\leq 4$  mm. Wide-neck is defined as having a neck width  $\geq 4$  mm or a dome-to-neck ratio  $< 2$ . The device must be used according to the Instructions for Use packaged with the study device, the study protocol inclusion and exclusion criteria, and the study procedures outlined in this study protocol.

### **6.2.2 Index Procedure**

For the ENTERPRISE Device see accompanying IFU for complete instructions including warnings and precautions, on intracranial stent preparation and usage. The index procedure (pre-treatment, intra-procedure, and immediate post-treatment of the index), 6 month and 12 month follow-up, any unscheduled and any pre-retreatment angiograms must be performed according to the study Core Lab Manual. Per the study protocol, the stenting and coiling must both be performed during the index procedure, and the embolization coils must be placed after the stent is deployed. Staged procedures are not allowed under this study protocol. If it becomes medically necessary to stage the stenting and coiling procedures this will be considered a treatment failure.

#### General Overview for ENTERPRISE Stent-Assisted Coiling

When delivering the stent under fluoroscopic visualization, the interventionist must slowly advance the delivery system to deploy the stent (See IFU for complete directions for use). Do not recapture the stent more than once. Optimal expansion requires the stent to be in full contact with the artery wall, with the stent internal diameter matching the vessel diameter. Stent wall contact should be verified through routine angiography. The interventionist must fully cover the entire aneurysm with the stent, allowing for adequate stent coverage into healthy tissue proximal and distal to the lesion (to maintain a minimum of 5 mm on either side of aneurysm neck). All efforts should be taken to assure that the stent is completely apposed to the vessel wall. Once the stent has been deployed, using the best orthogonal catheter arteriographic projections profiling the aneurysm relative to the parent artery, three orthogonal plane images of the stented artery must be obtained for independent core laboratory review. For size calculations using planar projections, sizing markers must be placed on both sides of the head due to the significant magnification that occurs.

After the stent has been deployed, remove and discard the delivery system. Verify that the stent has remained patent and properly positioned. After completing the procedure, withdraw and discard all

applicable accessory devices. The embolization coils must be placed after the stent is deployed, during the index procedure.

### 6.2.3 Embolic Devices

For the embolic device, refer to the enclosed labeling packaged with the embolic coils.

**Embolization Coils:** The embolization coils must be placed after the stent is deployed, during the index procedure. The protocol does not allow the use of Hydrocoils (the use of all other polymer coils, except Hydrocoils, are allowed). Any subject in whom a Hydrocoil is implanted will be considered a protocol deviation.

### 6.2.4 Procedure Assessments

(This is applicable to the index procedure as well as any other subsequent procedures)

#### **Start/End of Procedure:**

The following definitions apply to the index procedure.

- The start of the procedure is the time the femoral artery is accessed.
- The end of the procedure is the time the guiding catheter is removed from the subject.

#### **Procedural Study Assessments:**

- Procedural medications
- Event assessment during index procedure (pre-treatment, intra-procedure, and post-treatment), i.e. adverse events, protocol deviations, device malfunction/product complaint
- Angiogram
  - Upload or send the pre-treatment, intra-procedure, and post-treatment images to the study Image Management System

### 6.2.5 Procedural Medications

#### **Procedural Medications:**

Procedural medications administered in the pre-procedural, intra-procedural, and immediate post-procedural timeframes will be recorded on the eCRF. Procedure medications will include, antithrombotic, (including anti-platelet, anticoagulant, and fibrinolytics), and inhibitors of ADP-induced platelet aggregation medications that were administered within 7 days prior to the start of the procedure (femoral artery access) and up to and including 24 hours after end of the procedure (time guiding catheter is removed from the subject). Additionally, please indicate all **vasoactive** medications and **contrast**

that were administered intra-procedurally until the end of the index procedure.

**Post-Procedural Medications:**

Medications administered 24 hours after end of the index procedure will be recorded on the eCRF. Post-procedural medications will include all antithrombotics (including anti-platelet, anticoagulant, and fibrinolytics), and inhibitors of ADP-induced platelet aggregation medications.

The following post-index procedure medications are a requirement of this protocol.

- ASA (at least 81 mg/day) must be continued for a minimum of 12 months.
- P2Y12 Platelet Inhibitor must be taken daily for a minimum of 3 months

Please refer to Section 8 for further information concerning concomitant medications.

## 6.3 Follow-up

### 6.3.1 Follow-up of Angiographic Screening Failures

An angiographic screening failure is any subject who signed the study informed consent but meets any of the angiographic exclusion criteria as the screening procedure progresses. These subjects will not be entered in the study and will be followed for the period 72 hours following the end of the angiographic procedure to determine study angiographic eligibility or until discharge, whichever comes first. Any AEs that occur during this period must be documented. If any AE has not resolved by the 72-hour safety evaluation or discharge, follow-up must continue until resolution of the adverse event, after which they will be discontinued from the study.

For angiographic screening failures:

- Complete and enter onto Screening Log the reason why the subject was not eligible to participate in the study
- File the signed informed consent
- Complete and enter into database all eCRF up to and including the Investigator's angiographic assessment, these forms shall include:
  - Screening/Baseline
  - Pre-Procedure Angiography (and Pre-Treatment Angiography, if applicable)
  - Study Completion
  - Protocol Deviations, as applicable
  - Adverse Events, as applicable

- Complete and entered in the Adverse Event (AE) eCRF any AEs that occurred from the time the study informed consent was signed through the period 72 hours following the end of the angiographic procedure to determine study angiographic eligibility, or until discharge, whichever comes first, or to resolution of any adverse event, whichever is longer.

### 6.3.2 Follow-up After Stroke or Suspected Stroke (Unscheduled Visit)

If a subject experiences a stroke, or if there is any suspicion of a stroke, the subject needs to have an MRI completed within a time window of **24 hours after symptom(s) onset**.

Additionally, if the subject experiences a stroke they will need to return to visit the investigator 30 days (window 16 - 44 days) after the stroke for a neurological assessment to include, at a minimum, a modified Rankin Score (mRS) assessment and the National Institute of Health Stroke Scale (NIHSS).

In the event, that the subject experienced a stroke but the investigator did not learn about the stroke at the time it occurred, and thus an MRI was not done within 24 hours of the stroke, then site must obtain an MRI immediately upon learning of the stroke, as well perform the modified Rankin Score (mRS) assessment and the National Institute of Health Stroke Scale (NIHSS).

### 6.3.3 Post-Procedure through Hospital Discharge

All subjects entered into the study will undergo the following tests or procedures while in the hospital.

#### ***Assessment and subject interview***

- Vital Signs (Blood pressure, Heart Rate, and Respirations)
  - Immediately Post-Treatment
  - Hospital discharge
- Relevant Concomitant Medications (daily): indicate all antithrombotics (including anti-platelets, anticoagulants, and fibrinolytics), and inhibitors of ADP-induced platelet aggregation medications that were administered after 24 hours post-procedure through hospital discharge.
- Neurological assessment and evaluations performed by qualified personnel at 12-36 hours after end of procedure (removal of the guiding catheter from the subject). Included as part of this examination are the NIH Stroke Scale Score, Modified Rankin Scale, clinical neurological evaluation, and if applicable, the Hunt and Hess Scale (HHS) for subarachnoid hemorrhage

- Event assessment (daily) as applicable (i.e. adverse events, protocol deviations, device malfunction/product complaint).

#### **6.3.4 Thirty-Day Follow-up (Telephone Interview)**

The thirty-day follow-up visit must occur between 16 days to 44 days from the date of the index procedure and may be conducted via telephone.

All subjects entered into the study will be followed for adverse event assessment at thirty days.

All subjects entered into the study will be submitted to the following interview about their health condition and medications:

##### ***Subject interview***

- Relevant Concomitant Medications (daily since hospital discharge): indicate any antithrombotics (including anti-platelets, anticoagulants, and fibrinolytics) and inhibitors of ADP-induced platelet aggregation medications administered more than 24 hours post-procedure through end of study participation.
- Neurological evaluation performed by qualified personnel. Included as part of this examination is the Modified Rankin Scale.
- Event assessment (since discharge evaluation) (i.e., adverse events, protocol deviations, device malfunction/product complaint)

#### **6.3.5 6 Month Follow-up (Clinic Visit & Angiogram)**

The 6 month follow-up visit must occur between 92 days and 212 days from the date of the index procedure.

All subjects entered into the study will be followed for adverse event assessment at 6 months post-procedure.

The 6 month follow-up evaluations must be performed at the investigational site. All subjects entered into the study will be submitted to the following:

##### ***Assessment and subject interview***

- Vital Signs (Blood pressure, Heart Rate, and Respirations)
- Relevant Concomitant Medications (daily since 30 day follow-up): Indicate any antithrombotics (including anti-platelets, anticoagulants, and fibrinolytics) and inhibitors of ADP-induced platelet aggregation medications administered more than 24 hours post-procedure through end of study participation.
- Clinical Assessment and Physical Exam

- Neurological assessment and evaluations performed by qualified personnel. Included as part of this examination are the NIH Stroke Scale Score, Modified Rankin Scale, clinical neurological evaluation, and, if applicable, the Hunt and Hess Scale (HHS) for subarachnoid hemorrhage
- Event assessment (since 30 day follow-up) (i.e., adverse events, protocol deviations, device malfunction/product complaint)
- Angiogram
  - Upload or send the follow-up angiogram images to the study Image Management System
  - The 6 month follow-up angiogram shall be performed using the same orthogonal views as used during the index procedure, and according to the study Core Lab Manual.

### **6.3.6 12 Month Follow-up (Clinic Visit & Angiogram)**

The 12 month follow-up must occur between 320 days and 410 days from the date of the index procedure.

All subjects entered into the study will be followed for adverse event assessment at 12 months.

The 12 month follow-up evaluations must be performed at the investigational site. All subjects entered into the study will be submitted to the following:

#### ***Assessment and subject interview***

- Vital Signs (Blood Pressure, Heart Rate, and Respirations)
- Relevant Concomitant Medications (since 6 month follow-up): indicate any antithrombotics (including anti-platelets, anticoagulants, and fibrinolytics) and inhibitors of ADP-induced platelet aggregation medications administered more than 24 hours post-procedure through end of study participation.
- Clinical Assessment and Physical Exam
- Neurological assessment and evaluation performed by qualified personnel. Included as part of this examination are the NIH Stroke Scale Score, Modified Rankin Scale, clinical neurological evaluation, and, if applicable, the Hunt and Hess Scale (HHS) for subarachnoid hemorrhage.
- Event assessment (since 6 month follow-up) (i.e., adverse events, protocol deviations, device malfunction/product complaint)
- Angiogram
  - Upload or send the follow-up angiogram images to the study Image Management System
  - The 12 month follow-up angiogram shall be performed using the same orthogonal views as used during the

index procedure, and according to the study Core Lab Manual.

### **6.3.7 18 Month Follow-up (Telephone Interview)**

The 18 month follow-up visit telephone interview must occur between 457 days and 592 days from the date of the index stenting procedure.

The 18 month follow-up evaluations may be conducted via a telephone interview. All subjects entered into the study will be submitted to the following:

#### ***Subject interview***

- Relevant Concomitant Medications (since 12 month follow-up): indicate any antithrombotics (including anti-platelets, anticoagulants, and fibrinolytics) and inhibitors of ADP-induced platelet aggregation medications administered more than 24 hours post-procedure through end of study participation.
- Neurological evaluations performed by qualified personnel. Included as part of this examination is the Modified Rankin Scale.
- Event assessment (since 12 month follow-up) (i.e. adverse events, protocol deviations, device malfunction/product complaint)

### **6.3.8 24 Month Follow-up (Clinic Visit & MRA or Angiogram)**

The 24 month follow-up visit must occur between 685 days and 775 days from the date of the index stenting procedure.

The 24 month follow-up evaluations must be performed at the investigational site. All subjects entered into the study will be submitted to the following:

#### ***Assessment and subject interview***

- Vital Signs (Blood pressure, Heart Rate, and Respirations)
- Relevant Concomitant Medications (since 18 month follow-up): indicate any antithrombotics (including anti-platelets, anticoagulants, and fibrinolytics) and inhibitors of ADP-induced platelet aggregation medications administered more than 24 hours post-procedure through end of study participation
- Neurological evaluations performed by qualified personnel. Included as part of this examination are the NIH Stroke Scale Score, Modified Rankin Scale, clinical neurological evaluation, and, if applicable, the Hunt and Hess Scale (HHS) for subarachnoid hemorrhage
- MRI/MRA or angiogram (an angiogram must be performed if any stent or coils are not MRA/MRI compatible) to assess for in-stent stenosis, thrombosis and hydrocephalus, or if an angiogram is

- performed to assess for in-stent stenosis and thrombosis, then also obtain MRI or CT to assess for hydrocephalus)
- Event assessment (since 18 month follow-up) (i.e. adverse events, protocol deviations, device malfunction/product complaint)

Following the 24 month study visit, the subject will be discharged from the study. However, if the investigator determines there are indications of delayed hydrocephalus or in-stent stenosis occurring, additional follow-up may be required, including MRI or CT at the Investigator's discretion. If this should occur the investigator will determine the additional follow-up required at that time and inform the study sponsor.

If a subject presents with an adverse event at the 24 month follow-up, he/she will receive appropriate treatment for that condition. If the subject's condition precludes him or her from undergoing any 24 month evaluation specified by the protocol, the subject would be discharged from the study after the Investigator documents in the subject's medical record that a stable clinical endpoint has been reached, or that the subject's status is not associated with the device or procedure.

Subjects entered into the study will be considered eligible for follow-up unless they have died or withdrawn their consent to be contacted. The study center will review the follow-up requirements with the subject to help ensure compliance with the follow-up schedule. Telephone numbers should be obtained from the subject to ensure the ability to contact him or her at the required follow-up times. These phone numbers should include all home numbers, work numbers and primary physician numbers. A phone number of a relative or friend should also be requested.

### **6.3.7 Safety Follow-up (Subjects with Adverse Events of Special Interest)**

All subjects entered into the study who experience any adverse event of special interest and who have an MRS > 2 at any clinical evaluation will be followed through 24 months post-procedure, and their outcomes will be summarized in a supplemental safety follow-up report.

#### **Adverse Events of Special Interest include:**

- rupture of the index aneurysm beyond 24 hours post-treatment
- major ipsilateral stroke more than 1 month post-treatment
- ipsilateral parenchymal hemorrhage more than 1 month post-treatment
- device migration at the 6 month angiogram

## **6.4 Placement of Second ENTERPRISE Stent**

Per the study protocol inclusion and exclusion criteria, subjects are only expected to have one ENTERPRISE stent implanted. However, if upon initiating the index procedure, the Investigator deems it necessary to place an additional stent(s), the investigator must use an ENTERPRISE IDE stent. Placement of an additional stent(s) will be considered a protocol deviation.

- ***ENTERPRISE IDE stent should be used if placed in the target aneurysm***
- ***ENTERPRISE HDE stent should be used if placed in a non-target aneurysm]***

## 6.5 Retreatment of the Target Aneurysm

Retreatment in this study protocol, regardless whether by surgery or endovascular treatment, is defined as any additional treatment of the target aneurysm after the index procedure due to recanalization, rupture or bleeding, or as part of a staged procedure.

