### **3.2.3.6 Retreatment Rate**

The percentage of target aneurysms that are retreated at any time up to and including the 12 month follow-up visit will be evaluated. Retreatment will be defined as any additional treatment of the target aneurysm after the index procedure (retreatment includes staged procedures), or an additional procedure (regardless of whether retreatment is by surgery or endovascular treatment) due to recanalization, rupture or bleeding.

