**Retreatment Rate:**

The percentage of target aneurysms that are retreated at any time up to and including the 12 month follow-up visit will be evaluated. Retreatment will be defined as any additional treatment of the target aneurysm after the index procedure (retreatment includes staged procedures), and (regardless of whether retreatment is by surgery or endovascular treatment) due to recanalization, rupture or bleeding.

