## **RETREATMENT**

Retreatment will be defined as any additional treatment of the target aneurysm after the index procedure (retreatment includes staged procedures) and (regardless of whether retreatment is by surgery or endovascular treatment) due to recanalization, rupture or bleeding. The treatment session during which stenting of the aneurysm is attempted will be referred to as the “index” procedure.

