10.4.2.1 Secondary Effectiveness Endpoints

- Procedure success rate

The number and percentage of subjects who achieved procedure success will be summarized at immediately post-treatment (acute), 6-Month and 12-Month Follow-up visits.

- Rate of complete aneurysm occlusion

The number and percentage of subjects who have achieved complete aneurysm occlusion at immediately post-procedure (acute) and 6-Month Follow-up will be summarized based on the assessment from the Independent Core Laboratory.

- Complete/partial aneurysm occlusion as per the Raymond scale

The number and percentage of subjects who have reported a Raymond score of 1 (complete obliteration) or 2 (residual neck) will be summarized at immediately post-treatment (acute), 6-Month and 12-Month Follow-up Visits, based on the assessment from the Independent Core Laboratory.

- Percent aneurysm occlusion

The number and percentage of subjects by categories of aneurysm occlusion in percentage will be summarized at immediately post-procedure (acute), 6-Month and 12-Month Follow-up visits, based on the assessment from the Independent Core Laboratory.

- Recanalization rate

The number and percentage of subjects with recanalization up to and including 12-Month Follow-up Visit will be summarized based on the assessment from the Independent Core Laboratory.

- Retreatment rate

The number and percentage of subjects who received retreatments to the target aneurysms at any time up to and including 12-Month Follow-up will be summarized based on site reported data.

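### Protocol 6.5 counts retreatment only for listed causes or staging, while Protocol 3.2.3.6 and SAP 5.2.1 count any further treatment, so the site-reported retreatment rate could be too low

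*Protocol*

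**What the plan says.** The documents carry two versions of the definition.

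**Cause not required.** Protocol 3.2.3.6 reads "Retreatment will be defined as any additional treatment of the target aneurysm after the index procedure (retreatment includes staged procedures), or an additional procedure", and the sentence then attaches the listed causes to that second alternative only. The protocol overview (secondary effectiveness endpoint f) and SAP 5.2.1 use the same construction.

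**Cause required, or apparently required.** Protocol 6.5, in the study procedures chapter, reads "any additional treatment of the target aneurysm after the index procedure due to recanalization, rupture or bleeding", with a staged procedure as the only other route. Protocol 9.6 (Retreatment Rate) and two entries in Appendix 1 (Retreatment; Evolution of Aneurysm Occlusion) drop the second alternative and continue with "and (regardless of whether retreatment is by surgery or endovascular treatment) due to recanalization, rupture or bleeding".

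Three further provisions matter:

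- **Recanalization.** Protocol 3.2.3.5 and Appendix 1 define it as more filling that worsens the Raymond class.
- **Source of the rate.** SAP 10.4.2.1 counts subjects who "received retreatments to the target aneurysms at any time up to and including 12-Month Follow-up will be summarized based on site reported data".
- **Failure rule.** SAP 10.4.2 treats a subject retreated on or before an angiographic assessment as a failure for every secondary effectiveness endpoint except the retreatment rate itself.

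**The concern.** One endpoint has two definitions, and they disagree on a case that can plausibly arise: an aneurysm with a residual after the index procedure, unchanged at follow-up, that is then treated again. The narrower text sits in the chapter and the appendix that sites work from. The broader text sits in the endpoint chapter and the SAP. If a site does not report such a case as a retreatment, a broad definition at the analysis stage does not by itself recover it.

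Two results are exposed. The retreatment rate could be too low. An angiogram taken after a second treatment could also be scored as an outcome of the index treatment, although Protocol 4.0 ends effectiveness assessment of an aneurysm once it is retreated. Both errors would favour the device.

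**Working it through.** The plan gives no expected retreatment rate, so there is no figure to reproduce. The check is a comparison of texts.

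**Step 1. Test case.** A subject has a Raymond class 2 or 3 residual after the index procedure and the same class at 6 months. There is no rupture or bleeding. The target aneurysm is then treated again, and nobody records the second session as staged.

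**Step 2. Does the case meet a listed cause?** Recanalization needs a worse class, and the class is unchanged. Rupture and bleeding are absent by construction. No listed cause applies.

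**Step 3. Classification by section.**

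| Text | Is a cause required? | Test case |
|---|---|---|
| Protocol overview, endpoint f | No | Retreated |
| Protocol 3.2.3.6 | No | Retreated |
| SAP 5.2.1 | No | Retreated |
| Protocol 6.5 | Yes, unless staged | Not retreated |
| Protocol 9.6 | Can be read as yes | Not retreated on that reading |
| Appendix 1, two entries | Can be read as yes | Not retreated on that reading |

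The last two rows turn on one connective. In 3.2.3.6 the tail is a separate alternative: "or an additional procedure (regardless of whether retreatment is by surgery or endovascular treatment) due to recanalization, rupture or bleeding". In 9.6 and Appendix 1 it is joined by *and*, so the cause can be read as a condition on the whole definition.

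**Step 4. Which analyses use the classification?**

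- **Retreatment rate (SAP 10.4.2.1).** Used directly, from site reports.
- **Complete/partial occlusion and percent occlusion (SAP 5.2.1).** Neither SAP definition says that a further procedure disqualifies the subject. Within the SAP, the 10.4.2 failure rule is the only guard. The matching Appendix 1 entries in the protocol do carry such a clause.
- **Procedure success (SAP 5.2.1).** Has its own clause against further procedures.
- **Primary occlusion rate (Protocol 3.2.1, SAP 5.1.1).** Complete occlusion itself requires that no further procedure has been done on the aneurysm, with no limit on cause. The analysis rule in SAP 10.4.1.1 mentions only retreated subjects, but the definition still applies.

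**Step 5. Weight of one subject.** One reclassified subject moves a percentage by 100/n points. The SAP says the study stopped before reaching its planned 320, so n is below 320 and the shift exceeds 100/320 = 0.31 points per subject. The documents do not say how many subjects would be reclassified.

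**The case against.** The strongest reply is that the SAP governs the analysis and already has the right definition. A case is lost only if a site withholds it because of 6.5. The case report form wording is not in the documents, so that cannot be shown. Table 1 (footnote 5) and Protocol 6.2.4 also call for procedure data at any later procedure, whatever its label. A second session for a sac that never closed might be called staged: Appendix 1 defines staging as treatment completed over separate sessions, and 6.2.2 allows that it may become medically necessary. Finally, the *and* wording in 9.6 and Appendix 1 expressly includes staged procedures, which need not have a listed cause, so it may be a drafting slip.

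Most of this stands, and it limits the point to a risk. It does not remove the conflict. Section 6.5 is plainly narrow, the documents do not settle when a second session is staged, and the retreatment rate is tied to site reports and not to the procedure records.

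Two stronger readings are tempting, and neither is supported:

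- **That the understatement is large.** The sponsor's European registry (Protocol 1.3.4) found complete occlusion in 20.2% immediately after the procedure and 58.2% at 6 months, so 100 − 20.2 = 79.8% and 100 − 58.2 = 41.8% were not completely occluded. Those are rates of incomplete occlusion, not of retreatment or of a stable residual. The rise between the two time points shows more complete occlusion without saying anything about how often residuals were treated again. In that registry 34.3% had prior embolization or clipping, whereas this trial excludes previously treated target aneurysms.
- **That the primary occlusion rate is inflated against its performance goal.** That would require an analyst to disregard the endpoint's own definition. SAP sections 6 and 10.4 have also withdrawn the hypothesis tests, so there is no success decision to distort.

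**Conclusion.** The conflict is certain for Protocol 6.5 against Protocol 3.2.3.6, the overview and SAP 5.2.1. It is a reasonable reading of Protocol 9.6 and Appendix 1. Its consequence is a possible under-reporting of retreatment, with a possible knock-on effect on the secondary occlusion summaries that rely on the SAP 10.4.2 failure rule.

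Whether any case is lost depends on three things outside the documents: how the case report form words the question, which definition sites apply, and whether a second session for a residual is labelled staged. The size therefore cannot be estimated. The direction, if there is an effect, is toward a lower retreatment rate and fewer imposed failures. The primary occlusion rate is largely protected, and all results are descriptive. This should be corrected because the correction is cheap; it does not undermine the main result.

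**What to change.** 1. In Protocol 6.5, 9.6 and both Appendix 1 entries, adopt the meaning already in 3.2.3.6 and SAP 5.2.1: every further treatment of the target aneurysm once the index procedure is over, for whatever reason, staged sessions included.
2. In SAP 10.4.1.1, 10.4.2 and 10.4.2.1, derive one retreated flag from any procedure on the target aneurysm recorded after the index procedure, instead of relying on the site's use of the word retreatment. Table 1 footnote 5 and Protocol 6.2.4 already call for these records. Check that they identify the aneurysm treated.
3. Report the reason for each further treatment descriptively where it is available, so that readers can separate recanalization, rupture, bleeding, staging and persistent residual.

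The cost is a wording change and one derivation. The reported retreatment rate may be slightly higher. Because enrollment has ended early, the derivation in item 2 matters most: rewording the protocol does not recover procedures that sites have already left unreported as retreatments.
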